2.4 The subject participation time period

The subject participation period will be approximately 48 weeks. This will include a screening visit, 4 injection visits and 5 follow up visits. Total length of study/patient is 8.5 to 10.5 months.

Table 1. Visit Schedule

Screening Visit/V0

Selection of study TILs. Low-risk cSCC with at least 1 lesion > 0.5 cm to < 5 cm. TILs will have partial biopsies for confirmatory diagnosis. A total of up to 5 TILs per subject can be selected for treatment with no more than 3 lesions in one anatomical area. TILs in the same anatomical area will need to be 10 cm apart from the other injected lesions. A high frequency ultrasound of the TILs will be performed at baseline prior to starting first injection.

Selection of study TNILs. Lesions that are clinically suspicious of cSCC in the same anatomical location as TILs. Up to 10 TNILs can be followed with no more than 2 TNILs selected in the same anatomical area as a TIL. TNILs will have partial biopsies for confirmatory diagnosis. TNILs will be assessed by clinical measurement only without the use of ultrasound technique.

Visit 1: First Injection Visit: One to four (1-4) weeks after V0

- Target lesions (TILs and TNILs) are identified and documented with measurements and photographs. Photographs will be taken with regional and close up view of the anatomical area and lesion (Appendix A).
- Inject 0.1ml 4ml (based on TILs size section 7.1, Table 5) Talimogene laherparepvec at nominal concentration of 10⁶ plaque forming units (PFU)/mL with approximately 1.15 mL in a 2 mL vial for the initial dose. This will be administered intralesionally to 1-3 cSCC lesions per anatomical site with a maximum of 5 injectable lesions per patient.

Visit 2: Second injection visit: Three (3) Weeks after V1

- Target lesions are identified and documented with measurements and photographs. Photographs will be taken with global and close up view of the anatomical area and lesion (Appendix A).
- Inject 0.1ml 4ml (based on TILs size) and number of lesions selected.
 Talimogene laherparepvec at nominal concentration of 10⁸ PFU/mL with

approximately 1.15 mL in a 2 mL vial for the second and subsequent doses.

Visit 3: Third injection visit: Two (2) Weeks after V2

- Target lesions are identified and documented with measurements and photographs. Photographs will be taken with global and close up view of the anatomical area and lesion.

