6.1 Inclusion Criteria

- a. Able to give informed consent in English or Spanish
- b. Age > 18
- c. Have at least one >0.5 cm to <5.0 cm, histologically confirmed low risk cutaneous SCC (including kerathoacanthomas)
- Size >0.5 cm on trunk or extremities (excluding face, neck feet, nail units, and ankles)
- Clinically consistent with primary tumors.
- Lesion considered unresectable (as defined in Section 1.2)
- Recurrent lesions will be considered eligible if additional inclusion criteria are met.
- No immunosuppression
- Not a site of previous radiation therapy or chronic significant inflammation
- Fast growing lesions (doubling in size over a 4 week period of time) will be included if they are clinically suggestive of cSCC of the keratoacanthoma type.
- Well or moderately differentiated tumor as confirmed by skin biopsy
- Depth less than 2 mm (for non KA type cSCC)
- No perineural or vascular involvement in preliminary biopsy.
- d. Partial biopsy of squamous cell skin cancer identified as a target lesion(s) to determine the histological differentiation of the tumor or other adverse histological features
- e. In patients with multiple lesions, up to 3 lesions in a similar anatomical site, (trunk, limbs etc) that is at least 10 cm apart can be selected.
- f. Maximum of 5 lesions per patient can be selected for treatment
- g. Adequate organ function determined within 28 days prior to enrollment, defined as follows:
- h. Hematology:
- Absolute neutrophil count \geq 1500/mm3 (1.5x109/L)
- Platelet count ≥ 75,000/mm3 (7.5x109/L)
- Hemoglobin \geq 8 g/dL (without need for hematopoietic growth factor or transfusion support)
- i. Renal
- Serum creatinine ≤ 1.5 x upper limit of normal (ULN), OR 24-hour creatinine clearance ≥ 60 mL/min for subject with creatinine levels > 1.5 x ULN. (Note: Creatinine clearance need not be determined if the baseline serum creatinine is within normal limits. Creatinine clearance should be determined per institutional standard)
- j. Hepatic
- Serum bilirubin $\leq 1.5 \text{ x ULN}$
- Aspartate aminotransferase (AST) \leq 2.5 x ULN

- Alanine aminotransferase (ALT) \leq 2.5 x ULN
- k. Coagulation
- International normalization ratio (INR) or prothrombin time (PT) ≤ 1.5 x ULN, unless the subject is receiving anticoagulant therapy, in which case PT and partial thromboplastin time (PTT)/ activated PTT (aPTT) must be within therapeutic range of intended use of anticoagulants.

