- PTT or aPTT ≤ 1.5 x ULN unless the subject is receiving anticoagulant therapy as long as PT and PTT/aPTT is within therapeutic range of intended use of anticoagulants.

I. Female subject of childbearing potential should have a negative urine or serum pregnancy test within 72 hours prior to enrollment. If urine test is positive or cannot be confirmed as negative, a serum pregnancy test will be required.

6.2 Exclusion Criteria:

- a) Any patient with diagnosis of invasive cancer in the last 3 years with the exception of stage I and II melanoma, cutaneous BCC and SCCs will be excluded.
- b) Subjects on acitretin, capecitabine, topical chemotherapies or treatments. If participants have been on acitretin or capecitabine for up to 10 days, then no wash out period is required. If they have been on for more than 10 days, then they are required to do a wash out period of 30 days.
- c) Subjects on topical skin cancer directed therapies (fluorouracil, levulan-with photodynamic therapy, imiquimod, diclofenac, ingenol mebutate) will require a 30 days wash out window if applied withing the same anatiomic location. If applied at other anatomical sites a 10 days wash out period will be required.
- d) History or evidence of symptomatic autoimmune disease (eg, pneumonitis, glomerulonephritis, vasculitis, or other), or history of active autoimmune disease that has required systemic treatment (ie, use of corticosteroids, immunosuppressive drugs or biological agents used for treatment of autoimmune diseases) in past 2 months prior to enrollment. Replacement therapy (eg, thyroxine for hypothyroidism, insulin for diabetes or physiologic corticosteroid replacement therapy for adrenal or pituitary insufficiency) is not considered a form of systemic treatment for autoimmune disease.
- e) Evidence of clinically significant immunosuppression such as the following:
 - Primary immunodeficiency state such as Severe Combined Immuno deficiency Disease
 - Acquired immunodeficiency syndrome
 - Concurrent opportunistic infection
 - Receiving systemic immunosuppressive therapy (> 2 weeks) including oral steroid doses > 10 mg/day of prednisone or equivalent within 2 months prior to enrollment.
- f) Active herpetic skin lesions or prior complications of herpetic infection (e.g., herpetic keratitis or encephalitis).

- g) Requires intermittent or chronic systemic (intravenous or oral) treatment with an antiherpetic drug (e.g., acyclovir), other than intermittent topical use.

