6.3 Enrollment

All subjects who complete the screening period of the study will be enrolled and assigned a unique sequential subject identification number. This number will be used to identify the subject throughout the clinical study and will be used on all applicable study documentation related to that subject. The subject identification number will remain constant throughout the study.

The written informed consent document(s) must be signed and personally dated by the subject or by the subject's legally authorized representative and completed to a fully executed informed consent document and processed per the institution standard operating procedures.

Before subjects may be entered into the study, a copy of the written institutional review board (IRB) approval of the protocol, informed consent form (ICF), and all other applicable subject information and/or recruitment material must be on file at the institution.

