9.0 STUDY PROCEDURES

9.1 Screening- Visit 0

Potential subjects will enter the screening period of the study after a completely executed informed consent has been obtained.

- Review of inclusion/exclusion criteria
- Medical and medication history and dermatological history review
- Skin check by the study provider
- Urine pregnancy test (72 hours before enrollment)
- Screening blood work to include a complete blood count (CBC), comprehensive metabolic panel (CMP) and pregnancy test (hCG) if urine pregnancy test comes back positive or inconclusive
- Identification of the target lesions for the study. One subject can have up to 5 TILs. One to three TILs may be on the same anatomical area but will need to be 10 cm apart. Up to 10 TNILs can be followed with no more than 2 TNILs selected in the same anatomical area as a TIL.
- Photographing and measuring of the target lesions
- Biopsy of any suspected non-target skin cancers (ie BCC). If a non-SCC skin cancer is confirmed the corresponding treatment should be completed prior to initiation of study intervention.
- Partial biopsy of lesions suspicious for cSCC (both TILs and TNILs) that have not already been biopsied. A partial shave or small punch biopsy may be done to sample the tissue.
- Vital signs obtained to include blood pressure, pulse, temperature, height and weight
- Ultrasound of TILs at Radiology Department for baseline evaluation (Appendix B)
- Assign screening number starting with the 2-digit site number followed by SCC

and a 3-digit sequential number, starting with -001 and increasing by one for each subject. If a subject fails the screening visit they may be replaced by an additional subject.

9.2 Enrollment- Visit 1

• See 9.3 for enrollment visit details

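### Section 6.1 h prints two platelet cut-offs ten-fold apart, and the 72-hour pregnancy test (6.1 l) is listed only at Visit 0, at least four days before enrollment

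*Combined protocol and SAP*

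**What the plan says.** **Platelets.** Section 6.1 h requires "Platelet count ≥ 75,000/mm3 (7.5x109/L", closing the bracket after the litre unit. The neutrophil line just above it reads "1500/mm3 (1.5x109/L", in the same notation. In both, 109 stands for 10⁹ with the superscript lost.

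**Pregnancy test.**
- Section 6.1 l: "Female subject of childbearing potential should have a negative urine or serum pregnancy test within 72 hours prior to enrollment".
- Section 9.1 puts the test in the Visit 0 list with its own timing label: "Urine pregnancy test (72 hours before enrollment", followed by a closing bracket.
- The Section 26 table has one mark for the test, in the Visit 0 column. The Visit 1 list in Section 9.3 has no pregnancy test.
- The heading "9.2 Enrollment- Visit 1" places enrollment at Visit 1. Section 6.3 gives no other date and says only: "All subjects who complete the screening period of the study will be enrolled".
- Table 1 in Section 2.4 sets the gap: "Visit 1: First Injection Visit: One to four (1-4) weeks after V0". Section 9.3 gives 7 to 28 days, and Sections 9.3 and 9.7 allow 3 days either way.

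**Coagulation.** Section 6.1 g introduces the laboratory criteria with "Adequate organ function determined within 28 days prior to enrollment, defined as follows". Item k then sets limits for INR or PT and for PTT or aPTT. The screening blood work in 9.1 names a CBC, a metabolic panel and, if needed, a serum hCG. Footnotes 2 and 3 of Section 26 cover blood counts, chemistries and liver function. No visit list includes a coagulation test.

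**The concern.** A laboratory eligibility limit should have one value. Here the conventional-unit figure and the SI figure describe very different patients: anyone with a platelet count from 7,500 up to just under 75,000/mm³ fails one and passes the other. The criterion protects patients who have partial biopsies and up to four rounds of intralesional injection, and Table 6 lists injection site hemorrhage among the common reactions. Two sites work from this text.

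The pregnancy test raises a different question: whether the schedule can satisfy the criterion. Section 6.2 q excludes pregnant women, and 6.2 t names them among those at higher risk of HSV-1 complications. If staff test on the day that the Section 26 table marks, the result is out of date at the first dose, and the Visit 1 list contains no repeat.

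The coagulation point is smaller. The requirement is stated, so the risk is that a draw ordered from the visit lists omits it and the gap is found only when eligibility is completed at Visit 1.

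**Working it through.** **1. Platelet conversion**

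Inputs: the two lines in Section 6.1 h. Conversion: 1 L = 10⁶ mm³, so count per litre = count per mm³ × 10⁶.

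- Control, neutrophils: 1,500 × 10⁶ = 1.5 × 10⁹/L. The printed value is reproduced (ratio 1.0).
- Platelets: 75,000 × 10⁶ = 7.5 × 10¹⁰/L = 75 × 10⁹/L. The printed value is 7.5 × 10⁹/L and is not reproduced.
- Reading the bracket back: 7.5 × 10⁹ / 10⁶ = 7,500/mm³.
- Ratio: 75,000 / 7,500 = 10.

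The lost superscript is not the cause. Restoring 10⁹ in both lines makes the neutrophil line correct and leaves the platelet line wrong.

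**2. Timing of the pregnancy test**

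Inputs: limit 72 h (6.1 l); Visit 0 to Visit 1 of 7 to 28 days (Sections 2.4 and 9.3); window ±3 days (Sections 9.3 and 9.7); enrollment at Visit 1 (Section 9.2).

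Other text supports Visit 1 as the enrollment point. Section 6.3 gives enrolled subjects an identification number. Visit 0 assigns only a screening number, and the study number is assigned at Visit 1, where the inclusion and exclusion criteria are also completed.

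Hours past the limit = interval in days × 24 − 72, for a test on the Visit 0 day:

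| Visit 0 to Visit 1 | Days | Hours | Hours past 72 |
|---|---|---|---|
| Earliest with window (7 − 3) | 4 | 96 | 24 |
| Nominal minimum | 7 | 168 | 96 |
| Nominal maximum | 28 | 672 | 600 |
| Latest with window (28 + 3) | 31 | 744 | 672 |

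These figures count whole days. Clock times could shorten the 4-day gap by some hours, but it would still exceed 72 hours, because three full days lie between the two dates. No permitted timing of Visit 1 brings a Visit 0 test inside the limit.

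**3. Coagulation and the 28-day limit**

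Item k requires two tests (INR or PT; PTT or aPTT). The number listed in Sections 9.1, 9.3 and 26 is zero. The latest permitted Visit 1 is day 31 against the 28-day limit in item g: 31 − 28 = 3 days. Blood drawn on the Visit 0 day is thus 1 to 3 days out of window if Visit 1 falls on days 29 to 31.

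**The case against.** On platelets, the best reply is that 75,000/mm³ comes first, in the same unit as the neutrophil line, and is plainly the working figure. Only the bracketed conversion is wrong, and nothing shows that a site would use it. This is fair as to intent and makes actual harm unlikely. It does not remove the error: the line states two limits and does not say which governs.

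On the pregnancy test, the reply is stronger. Section 9.1 carries the 72-hour label itself, and both 9.1 and 6.3 describe screening as a period. The 9.1 list also includes a Radiology ultrasound and treatment of any confirmed non-SCC skin cancer, so it need not be a single-day list. A test in the last 72 hours of screening complies, and completing eligibility at Visit 1 should expose a stale result. All of that stands: the criterion can be met, and the overruns in the table apply only to a test on the Visit 0 day. What remains is that no listed visit falls in the last 72 hours. Compliance needs a contact or a repeat test that the schedule does not provide, and the Section 26 table points staff to the wrong day without a timing footnote.

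On coagulation, items g and k already impose the requirement, and the blood-work lists need not be exhaustive. Likewise, the 28-day limit overrides the outer edge of the visit window, so a late Visit 1 calls for a repeat draw and is not a contradiction. Both replies are sound, and this part is a minor omission from the schedule.

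**Conclusion.** The point holds.

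- **Platelets:** certain. The two printed limits, 75 and 7.5 × 10⁹/L, differ by a factor of 10. That 75,000/mm³ is the intended one is a reasonable inference, not something the document states.
- **Pregnancy test:** the criterion and the schedule do not fit. The size, 24 to 672 hours past the limit (96 to 600 at nominal timing), rests on enrollment at Visit 1, as in Section 9.2, and on testing on the Visit 0 day, as the Section 26 table marks it.
- **Coagulation:** two required tests, none listed; minor.

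The likely consequences are eligibility deviations and repeat testing. Nothing here touches the Simon two-stage design, the primary endpoint, alpha or power. The sponsor should correct it, mainly because the limits concern safety and the correction is simple.

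**What to change.** 1. **Section 6.1 h:** change the bracketed platelet value to 75 × 10⁹/L. No cost.
2. **Section 6.1 l:** schedule the pregnancy test at Visit 1 before injection, or in the 72 hours before it. Say so in Sections 9.1 and 9.3, and mark it in the Section 26 table. The cost is moving one test.
3. **Section 6.1 k:** keep the criterion. Add INR/PT and PTT/aPTT to the screening blood work in Sections 9.1 and 26, drawn within 28 days before Visit 1, with a repeat if Visit 1 falls on days 29 to 31 after the draw. The cost is two assays on an existing draw, plus an occasional repeat.

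One short amendment covers all three, with no change to sample size, alpha or power.

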6.3 Enrollment

All subjects who complete the screening period of the study will be enrolled and assigned a unique sequential subject identification number. This number will be used to identify the subject throughout the clinical study and will be used on all applicable study documentation related to that subject. The subject identification number will remain constant throughout the study.

The written informed consent document(s) must be signed and personally dated by the subject or by the subject's legally authorized representative and completed to a fully executed informed consent document and processed per the institution standard operating procedures.

Before subjects may be entered into the study, a copy of the written institutional review board (IRB) approval of the protocol, informed consent form (ICF), and all other applicable subject information and/or recruitment material must be on file at the institution.

7.0 STUDY PLAN

7.1 IP/treatment regimen

The recommended volume of talimogene laherparepvec to be injected into the tumor(s) is dependent on the size of the tumor(s) and should be determined according to the injection volume guideline in Table 5. The maximum dose to be given is 4.0 ml per injection visit.

Table 5: Talimogene Laherparepvec Injection Volume Guideline Based on Tumor Size

Tumor Size (longest dimension)	Maximum Injection Volume
> 5.0 cm	4.0 mL
> 2.5 cm to 5.0 cm	2.0 mL
> 1.5 cm to 2.5 cm	1.0 mL
> 0.5 cm to 1.5 cm	0.5 mL
> 0.1 to 0.5 cm	0.1 mL

7.2 **Pre-medications**

There are no medications that need to be taken before the injections however the patient will be given the choice to take Ibuprofen or acetaminophen prior to the injections.

7.3 **Rescue Medications – Not applicable**

7.4 Excluded medications/treatments

The following medications and treatment are excluded during the entire study participation including follow up visits.

- Oral medications: Acitretin, xeloda, vismodegib, and niacin/nicotinamide (see wash out periods for certain medications).
- Topical medications at the anatomical study site: fluorouracil, levulan (with photodynamic therapy), imiquimod, diclofenac, ingenol mebutate.
- Injectable medications: Fluorouracil (Adrucil) on the anatomical area of the targeted cSCC) during active participation in the study.

Subjects can re-initiate systemic intervention once Visit 8 is completed.

8.0 **REQUIREMENTS FOR TREATMENT**

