- Inject 0.1ml 4ml (based on TILs size) and number of lesions selected.
 Talimogene laherparepvec at nominal concentration of 10⁸ PFU/mL with approximately 1.15 mL in a 2 mL vial for the subsequent doses.

Visit 4: Fourth injection visit: Two (2) Weeks after V3

- Target lesions are identified and documented with measurements and photographs. Photographs will be taken with global and close up view of the anatomical area and lesion (Appendix A).
- Inject 0.1ml 4ml (based on TILs size) and number of lesions selected.
 Talimogene laherparepvec at nominal concentration of 10⁸ PFU/mL with approximately 1.15 mL in a 2 mL vial for the subsequent doses.

Visit 5: First Follow up visit: Four (4) weeks after V4

 Target lesions are identified and documented with measurements and photographs. Photographs will be taken with global and close up view of the anatomical area and lesion (Appendix A).

Visit 6: Second Follow up visit: Four (4) weeks after V5

 Target lesions are identified and documented with measurements and photographs. Photographs will be taken with global and close up view of the anatomical area and lesion (Appendix A). A repeat high-frequency ultrasound of target lesions will be completed to assess response from baseline.

Visit 7: Third Follow up visit: Six (6) weeks after V6

• Target lesions are identified and documented with measurements and photographs. Photographs will be taken with global and close up view of the

anatomical area and lesion (Appendix A).

Visit 8: Fourth Follow up visit: Fourteen (14) weeks after V7

• Target lesions are identified and documented with measurements and photographs. Photographs will be taken with global and close up view of the anatomical area and lesion (Appendix A).

Visit 9: Telephone Follow up: twelve (12) months after first injection (V1)

• Research coordinator will assess patient over the phone to determine if any changes have occurred to target lesions after V8.

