9.4.3 Chart Review: Frequency of Nonmelanoma Skin Cancers (NMSCs)

Participants' charts will be reviewed to assess the number of nonmelanoma skin cancers before and after the intervention. The frequency of NMSCs before the intervention will include the 12 months before Visit 1 and the 24 months before Visit 1 if available. The frequency of NMSCs after the intervention will include the 12 months after the last injection visit (or Visit 4) and then 24 months after the last injection (or Visit 4) if available. This exploratory objective is an effort to quantify the abscopal effect those participants may experience.

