16.2.8 Chart Review of Abscopal Effect

Summary statistics (counts, percentage, mean, standard deviation, etc.) will be presented for exploratory endpoint as appropriate. Statistical comparison of the number of non-melanoma skin cancers in the 12 month and 24 month period prior to the TVEC injections versus the number in the 12 months after the TVEC injections will be performed using the Wilcoxon Rank Sum Test.

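### The exploratory before/after skin-cancer count can be confounded by other skin-cancer drugs, which the protocol stops and then releases part-way through the window tested

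*Combined protocol and SAP*

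**What the plan says.** Sections 9.4.3 and 16.1.3 count NMSCs from charts, with no restriction on body site, over 12 and 24 months before Visit 1 and over 12 (if available, 24) months after Visit 4. Both present the exercise as quantifying the abscopal effect. Section 16.2.8 plans summary statistics and a Wilcoxon rank sum test: "Statistical comparison of the number of non-melanoma skin cancers in the 12 month and 24 month period prior to the TVEC injections" against the number in the 12 months after. It mentions no other treatment.

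The drug rules are as follows.

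- **Before entry.** Section 6.2 b requires a 30-day washout after more than 10 days on acitretin or capecitabine, and none after shorter use. Section 6.2 c requires 30 days for topical agents in the same anatomical location; for use elsewhere, "If applied at other anatomical sites a 10 days wash out period will be required".
- **On study, opening rule of 7.4.** "The following medications and treatment are excluded during the entire study participation including follow up visits". The oral agents named are acitretin, capecitabine (by brand name), vismodegib and niacin/nicotinamide.
- **On study, topical agents in 7.4.** "Topical medications at the anatomical study site: fluorouracil, levulan (with photodynamic therapy), imiquimod, diclofenac, ingenol mebutate". Use at other body sites is not listed.
- **Release in 7.4.** "Subjects can re-initiate systemic intervention once Visit 8 is completed".

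The schedule in section 26 marks concurrent medications at every visit to Visit 8 and at early termination, but not at the telephone follow-up.

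**The concern.** A before/after count can be read as a treatment effect only if other influences on the count are similar in both windows. Here the protocol itself changes one of them. Subjects may arrive on drugs directed at skin cancer, must stop the systemic ones, and may restart them part-way through the after window. The release sentence speaks of re-initiating, which presupposes earlier use. Topical treatment away from the study site, where new cancers would also count, is not barred at any time after entry.

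Forced withdrawal can raise the after count and hide a benefit. A start after Visit 8, or topical treatment elsewhere, can lower it and imitate one. The comparison bears on the hypothesis in section 4.1 of a systemic anti-tumour response beyond the injected lesion. Under the plan as written, a drug-driven change could be credited to, or held against, talimogene laherparepvec, and the scheduled visits would not supply the exposure data needed to tell the difference.

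**Working it through.** The documents give no effect size, power or sample size for this endpoint, so there is no planned figure to reproduce. The check is of the timeline, followed by an illustration under stated assumptions.

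**Timeline** (section 2.4, Table 1; windows from section 9.7)

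- Visit 4 to Visit 8: 4 + 4 + 6 + 14 = 28 weeks (196 days).
- 12-month after window: 52 weeks from Visit 4. Systemic agents are barred for 28 weeks and unbarred for 52 − 28 = 24 weeks; 24/52 = 46%.
- With all visit windows stacked (7 + 7 + 10 + 21 = 45 days), Visit 8 falls 151 to 241 days after Visit 4. The unbarred share is then (365.25 − 241)/365.25 = 34% to (365.25 − 151)/365.25 = 59%.

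**One subject, no true effect.** Let r be the NMSC rate on the agent relative to off it. Assumed values, not in the documents: r = 0.5 (50% reduction) and r = 0.7 (30% reduction).

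1. On the agent all year before, off to Visit 8, then on again: (28 + 24r)/(52r) − 1.
   - r = 0.5: 40/26 − 1 = +54%.
   - r = 0.7: 44.8/36.4 − 1 = +23%.
2. The same, with a 30-day washout (30/7 = 4.3 weeks) before Visit 1, leaving 47.7 treated weeks: (28 + 24r)/(47.7r + 4.3) − 1.
   - r = 0.5: 40/28.15 − 1 = +42%.
   - r = 0.7: 44.8/37.69 − 1 = +19%.
3. Not on the agent before, starts at Visit 8: (28 + 24r)/52 − 1.
   - r = 0.5: 40/52 − 1 = −23%.
   - r = 0.7: 44.8/52 − 1 = −14%.

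Case 1 fits only agents with no listed washout (vismodegib, nicotinamide). Case 2 is the relevant one for acitretin or capecitabine taken for more than 10 days.

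**Whole group, no true effect.** Let q be the rate reduction (assumed 10% to 50%), s the share of subjects using an agent (assumed 50% to 100%), and f = (365.25 − 196)/365.25 = 0.463 the unbarred share. Users and non-users are given the same underlying rate, and no washout is applied.

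| Pattern | After/before ratio, 12 months | q = 0.1, s = 0.5 | q = 0.5, s = 1 |
|---|---|---|---|
| Starts after Visit 8 | 1 − sqf | 0.98 | 0.77 |
| On before, off to Visit 8, resumes | (1 − sqf)/(1 − sq) | 1.03 | 1.54 |

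The distortion at 12 months therefore runs from 2–3% to the single-user extremes, in either direction. With few users it is smaller still, and with none it is zero.

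**The case against.** The case on the other side is substantial.

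- **Permission is not use.** A reader might infer that the after counts do mix treated and untreated time. The documents show only that they can: nothing says how many subjects, if any, restart. This stands. What is certain is the split of the window into barred and unbarred time.
- **The large percentages describe one full-time user.** They rest on assumed drug effects, and the largest ignores the acitretin/capecitabine washout. This stands, which is why the lower figures and the group range are given.
- **The 24-month after window.** There, 76 of 104 weeks (73%) are unbarred, and a reader might take that as the main figure. But 16.2.8 tests only the 12-month after count; the longer one is collected if available.
- **Exposure is partly recorded.** Section 9.1 takes a medication history at screening, and medications are reviewed at each visit to Visit 8. That covers the barred 28 weeks. The gap is dated exposure in the earlier windows and after Visit 8.
- **The disagreement in 7.4 is minor.** The release sentence can be read as saying when the systemic bar ends, and section 9.5.1 treats participation as complete at Visit 8 if sites are free of disease. Yet section 2.4 counts five follow-up visits, which include the Visit 9 call, so the two end points still need reconciling.
- **Drug-free subjects do not rescue the inference.** A reader might infer that participants who used no such agent would show the abscopal effect cleanly. They would not. Restarting may be prompted by new cancers, so excluding those who restart can remove high after counts and imitate a benefit. Regression to the mean and time trends also remain in a single-arm before/after count.

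**Conclusion.** The concern holds as a possible confounding of an exploratory comparison. The before windows may include treated time, systemic agents are barred for only 28 of the 52 weeks tested (46% unbarred; 34% to 59% across visit windows), topical agents away from the study site are never barred after entry, and 16.2.8 takes no account of any of this.

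Direction and size cannot be fixed from the documents. Under an assumed 50% (30%) rate reduction, one user shows up to +54% (+23%) on stopping and resuming, about +42% (+19%) if a 30-day washout falls before Visit 1, and −23% (−14%) on starting at Visit 8. The group effect scales with the unknown share of users.

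The documents do not support saying that the comparison is already biased, or that the trial's main conclusion is at risk: the endpoint is exploratory and the primary response rate does not depend on it. They do support saying that the raw difference should not be labelled abscopal. This is a minor point with an inexpensive remedy.

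**What to change.** No change of clinical rule is needed for the analysis.

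1. **Section 9.4.3.** Abstract from the same charts the start date, stop date and body site of every agent listed in 7.4, in each counting window.
2. **Section 16.2.8.** Keep the all-participant comparison and show three sensitivity analyses beside it:
   - counts by time on and off such agents;
   - Visit 4 to Visit 8 against an equal period (nominally 28 weeks) before Visit 1, noting that this makes the systemic rule uniform only on the after side;
   - participants with no such agent in the windows compared, noting that this subset is small and selected on post-treatment behaviour.
3. **Sections 9.4.3, 16.1.3 and 16.2.8.** Describe the result as a change in NMSC frequency, not as an abscopal effect.
4. **Section 7.4.** Reconcile the two stated end points of the exclusion (all follow-up visits, or Visit 8). Which one applies is for the sponsor to decide.

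The cost is a few extra chart-review fields and some wording. The subgroups will be small: about 20 subjects are planned, and 7 if the trial stops at its first stage. Charts may also record topical use incompletely, so the sensitivity analyses can limit a wrong conclusion but cannot establish a cause.
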